Surgery and hospital admission (T8): Surgery will take place in the habitual waiting timeframe and will be performed by the regular cardiac surgery teams present in Hospital Clinic de Barcelona. Perioperative clinical protocols will be followed in a usual fashion independently of the group allocation or study participation. Hospital staff, anesthesiologists, surgeons, nurses and other people involved in patient care will be blinded to the study arm. Intraoperative complications or events as well as the need blood product transfusion or any deviation from normal course will be recorded in the intraoperative case report form (CRF).

The primary outcome of this study is the incidence of postoperative complications before patient discharge from the hospital. The type of complications included will be classified following the standards of the European Society of Anesthesiology and the European Society of Intensive Care medicine: Acute kidney injury, acute respiratory distress syndrome, arrhythmia, cardiac arrest, cardiogenic pulmonary oedema, deep vein thrombosis, delirium, gastrointestinal bleed, infection, source uncertain, laboratory confirmed bloodstream infection, myocardial infarction, pneumonia, paralytic ileus, post-operative haemorrhage, pulmonary embolism, stroke, surgical site infection and urinary tract infection.

The severity of complications will be also recorded, as a secondary outcome measure, following the Clavien- Dindo classification. To ensure accuracy of the primary endpoint, the data will be collected by a physician member of the team, every day according to standard clinical care, and then reviewed by another researcher. Both of them will be

blinded to the study group to avoid bias. Patient- chargeable costs (ie, pharmacy and blood bank); tariff- chargeable costs (ie, medical care, diagnostic techniques, laboratories, interconsultations); other healthcare resources use (ie, ICU stay, total hospitalisation length of stay, readmissions, emergency room visits) and survival will be also assessed at 3 months and 1 year postcardiac surgery by chart review.

Data collection management and monitoring: All participant's de-identified data collected at different time points will be entered by research staff members into Research Electronic Data Capture (REDCap) CRF via a secure webpage interface. Online data will be stored in a safe server located the Hospital

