Data monitoring: Previous experiences in prehabilitation studies show a clear absence of safety problems related to the experimental procedure. In addition, it is an unmasked trial, which is easier and faster to detect a problem and take appropriate measures.

The investigators of the present study are responsible for ensuring that the study meets the proposed milestones and deadlines. They will also be responsible for all aspects of the study design, management, ethical conduct, analysis and dissemination of results.

Safety data, including new hospitalisation, worsening angina or heart failure and arrhythmias, will be captured and all adverse events will be reported. They are responsible to periodically evaluate the study data for participant safety and study conduct, in addition to making modifications and/or termination of the trial after communication to the Ethics Committee of Clinical investigation of Hospital Clinic de Barcelona.

- *Outcomes*

Clinical outcomes

The primary outcome variable of the study is the incidence of postoperative complications classified following the standards of the European Society of Anaesthesiology and European Society of intensive Care Medicine.

Secondary outcome variables will be: (1) severity of postoperative complications using Dindo-Clavien classification; (2) hospital and ICU days of stay and (3) 3-month and 1-year mortality. Other outcome variables include: (1) ET measured by a cycling constant work-rate exercise testing at 80% of peak oxygen uptake; (2) distance covered in the 6MWT; (3) STS test and hand-grip strength; (4) physical activity by the YPAS and (5) hospitalisation direct costs and use of healthcare resources into the follow-up 1-year period after surgery.

Outcomes for feasibility of prehabilitation include incidence of adverse events during training, compliance to the supervised training sessions and adherence to the programme.

- *Statistical analyses*

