Sample size for this trial has been calculated based on the primary outcome of the study that is the reduction of incidence of postoperative complications in the prehabilitation group. Our own data in a similar population of patients indicated that the incidence of postoperative complications was 30%. Accepting a two-sided alpha-risk of 0.05 and beta-risk of 0.20, anticipating 10% of drop-outs, indicated the need of including 80 participants per group to detect a reduction of the percentage of patients with complications in the intervention group compared with the control group 20%. No adjustment for multiplicity was proposed due to this is a clinical trial with one primary outcome and without needed of interim analyses.

This trial will use intention-to-treat criteria for main analysis; nevertheless, analysis per protocol will also be performed as supportive analysis. Categorical variables, as well primary outcome, will be analysed with Fisher's exact test. Continuous variables will be compared with Student's t-test for independent groups and Mann-Whitney U test according to each variable distribution. Ordinal variables will be analysed by Mann-Whitney U test.

Secondary outcomes looking at the difference between groups for the change in functional capacity over the different time points (repeated measures) will be analysed using generalized estimating equations models and will be shown as estimated effect and their 95%CI. For these analyses, we will apply unstructured matrix in order to assess intra-subject correlation, for cases with no adjustments we will apply an autoregressive model (AR) (1) type matrix.

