A cost-effectiveness study will be carried out from the perspective of the hospital, taking into account the costs of the intervention and the expenses related to the disease during the follow-up (30 days). For costs, the mean or median and their 95%CI of difference in per-patient costs between the two groups will be computed (control-group costs minus prehabilitation-group costs), so that positive values will be interpreted as savings of the prehabilitation programme. Considering previous experience with prehabilitation cost analysis, a highly skewed distribution will probably be present. Right-sided asymmetric distribution appears when some patients incur in high costs, mainly because of major medical complications. To deal with this, a non-parametric approach (bootstrapping) will be used. Bootstrap analysis yields more robust when dealing with skewed cost data compared with non-parametric tests.

- Perioperative neurocognitive disorders subproject

Inclusion criteria: Patients included in the main study with age ≥ 50 years.

Exclusion criteria: Those applied for the main study. Additionally, reading difficulties, and non-Spanish or Catalan native speakers will also be excluded.

Baseline cognitive assessment (T0): We selected a battery of tests with input from a neurologist and a neuropsychologist – both experts on cognitive disorders. Two blinded-trained professionals ([name]) will perform the cognitive assessment in a quiet

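### Subproject 2 lets savings be a mean or a median cost difference, but only the mean difference equals the change in the hospital's bill (minor)

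*Combined protocol and SAP*

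**What the plan says.** All references are to the combined protocol and SAP, Subproject #2.

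- **Statistical analyses, viewpoint and content:** "A cost-effectiveness study will be carried out from the perspective of the hospital, taking into account the costs of the intervention".
- **Statistical analyses, summary measure:** "For costs, the mean or median and their 95%CI of difference in per-patient costs between the two groups will be computed". The difference is control minus prehabilitation, "so that positive values will be interpreted as savings of the prehabilitation programme".
- **Statistical analyses, skew:** strong right skew is expected. "Right-sided asymmetric distribution appears when some patients incur in high costs, mainly because of major medical complications". The stated response is to bootstrap. The statistic to be bootstrapped is not named.
- **Outcomes:** the cost item is the fifth of the other outcome variables, after the primary and secondary ones: "hospitalisation direct costs and use of healthcare resources into the follow-up 1-year period after surgery".

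Nothing else in Subproject 2 settles the choice. Its rule of t-test or Mann-Whitney according to distribution selects a test, not a cost summary. Subproject 1 describes costs by median (IQR), but that is a different study.

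**The concern.** A saving to the hospital is a change in a total. Totals follow from means and not from medians. The plan allows either and attaches the word savings to whichever is reported. If both are reported, it does not say which one decides.

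The plan's own account of the skew is why this matters. High costs come mainly from major complications, and the programme aims to reduce complications. With complication rates well below 50% in both arms, the median falls mostly among uncomplicated patients. It therefore registers little of the money saved in the tail, yet it carries the full programme cost, which every treated patient incurs. The size of the reported saving, and sometimes its sign, can then depend on a choice that could be made after the costs are seen.

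**Working it through.** **1. Complication rates, from the plan's sample size.** Inputs (Statistical analyses): control rate 30%, reduction 20%, two-sided alpha 0.05, power 80%, drop-out 10%, 80 per group. Read as 30% versus 10%:

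- n = [1.96·√(2·0.2·0.8) + 0.842·√(0.3·0.7 + 0.1·0.9)]² / 0.2² = 61.6
- with continuity correction: (n/4)·[1 + √(1 + 4/(0.2n))]² = 71.2, so 72
- 72/0.9 = 80, the plan's figure

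A fall from 30% to 24% would need 859 or 892 per arm before drop-out (without or with the correction). So 30% versus 10% is used below.

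**2. The identity.** Total cost of N patients = N × mean cost, so the change in the bill is N × (control mean − prehabilitation mean). No such relation holds for medians. Hand example with assumed costs: uncomplicated 10, complicated 30, programme 1.

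- Means: 0.7·10 + 0.3·30 = 16, and 0.9·10 + 0.1·30 + 1 = 13. The saving is 3 per patient, or 300 per 100 patients.
- Medians: 10 and 11. The difference is −1, which would be read as a loss.

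**3. Illustration when complications are reduced.** All costs are assumptions: uncomplicated stay log-normal with median EUR 15,000 and log-SD s = 0.2, 0.3 or 0.5; costly complication m = 2, 3 or 4 times that; programme EUR 500 or 1,500. This gives 18 settings. With q the proportion of patients having a costly complication:

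- mean = 15,000·exp(s²/2)·(1 − q + q·m)
- the median x solves (1 − q)·Φ(ln(x/15,000)/s) + q·Φ(ln(x/(15,000·m))/s) = 0.5
- the programme cost is added to both in the prehabilitation arm

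The two extremes when every complication is costly (q = 0.30 versus 0.10):

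- s = 0.2, m = 2, EUR 1,500: means 19,894 − 18,333 = 1,561; medians 16,790 − 16,925 = −135; ratio −8.6%
- s = 0.5, m = 2, EUR 500: means 22,096 − 19,197 = 2,899; medians 18,118 − 16,359 = 1,759; ratio 60.7%

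The middle value of the 18 ratios is 25%. The plan does not say what share of complications is costly, so that share is varied:

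| Share costly | q, control vs prehabilitation | Mean saving positive (of 18) | Of those, median shows none | Mean minus median difference, EUR |
|---|---|---|---|---|
| 100% | 30% vs 10% | 18 | 3 | 1,140 to 7,809 |
| 50% | 15% vs 5% | 18 | 12 | 760 to 4,106 |
| 30% | 9% vs 3% | 15 | 12 | 496 to 2,494 |
| 20% | 6% vs 2% | 12 | 12 | 343 to 1,671 |

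The ends of the first row are 2,899 − 1,759 and, at s = 0.2, m = 4, EUR 500, 8,682 − 873. Its three reversals all occur at s = 0.2 with the EUR 1,500 programme and are small (EUR −127 to −135).

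**4. The opposite case.** Complications 30% in both arms, cost of complicated stays unchanged, uncomplicated median EUR 2,000 lower, programme EUR 1,500:

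- s = 0.2: mean difference 0.7·2,000·exp(0.02) − 1,500 = 1,428 − 1,500 = −72
- s = 0.3: 0.7·2,000·exp(0.045) − 1,500 = 1,464 − 1,500 = −36
- median difference over the same settings: +701 to +870

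The hospital loses money while the median shows a saving. At s = 0.5 the mean difference is 1,586 − 1,500 = +86, so the sign does not reverse there.

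**5. How far the opposite case depends on its condition.** Ratio of median to mean difference before programme cost, uncomplicated stays EUR 1,000, 2,000 or 3,000 cheaper (27 settings):

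| Complicated stays | Ratio |
|---|---|
| cost unchanged | 1.21 to 1.62 |
| cheaper by the same euro amount | 0.95 to 1.14 |
| cheaper in the same proportion | 0.58 to 0.86 |

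If the programme only adds a constant cost and changes nothing else, the two measures agree.

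**The case against.** The strongest reply is that the plan meets skew by bootstrapping, in preference to non-parametric tests, and nowhere says that it will switch to medians. Its wording can also be read as a promise to report both summaries. A reader might infer that the trial will judge savings on the median; the documents do not say so. This stands and lowers the severity. What remains is that the median is permitted and nothing says which summary is meant by savings.

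Every cost above is invented. That is true, but the conclusion rests on the identity, and the figures only show possible size. Treating every complication as costly is also generous, because the primary outcome includes milder events ("pneumonia, paralytic ileus, post-operative haemorrhage, pulmonary embolism, stroke, surgical site infection and urinary tract infection") while the plan blames major complications for high costs. Hence the split by costly share. The euro gap shrinks as the share falls, but so does the mean saving.

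A reader might infer that the median overstates savings whenever uncomplicated care becomes cheaper. That is too general: it needs the cost of complicated stays to be unchanged, and no section says that savings would reach only uncomplicated patients.

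A reader might also infer that a formal savings verdict would change with the choice. The plan sets no threshold and does not require the interval to exclude zero.

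The cost analysis uses 30 days and the outcome list 1 year. These may be two separate analyses. This is a different wording matter and forms no part of this point.

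**Conclusion.** The point holds as a minor one. The plan leaves open which statistic defines a saving to the hospital, and only the arithmetic mean difference measures it. This part needs no assumption about costs.

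Direction and size do need assumptions. Under the mechanism that the plan describes, understatement by the median is the likelier error. Overstatement is possible only under narrower conditions. Sign reversal is uncommon and close to zero when every complication is costly. It is frequent in the assumed settings when half or fewer are.

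The primary comparison and the 80 per group are untouched.

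**What to change.** In the cost paragraph of Subproject 2, Statistical analyses, state that savings means the difference in arithmetic mean cost per patient, control minus prehabilitation with the programme cost included, reported with a bootstrap 95% CI. Keep medians (IQR) to describe the typical patient, without the word savings.

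This is a wording change only. The data and the bootstrap are already planned. The price is precision: in simulations of the settings with every complication costly, at 72 analysed per arm, the sampling SD of the mean difference was about 1.0 to 2.9 times that of the median difference. A wider interval around the right quantity is the better trade, and the medians remain available beside it.
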